- 4) Able and willing to provide informed consent to participate in this study

As evaluation of above inclusion criteria, the ejection fractions must be measured by angiography, radionuclide scanning, or echocardiography, and MI's must be documented and defined according to the consensus document of the Joint European Society of Cardiology/American College of Cardiology Committee for the Redefinition of Myocardial

Infarction Ejection fraction must be measured within 6 months of consenting to be considered eligible for entry. This study will allow the recruitment of inpatients.

B. Exclusion Criteria

All patients satisfying the inclusion criteria will be excluded for any of the following criteria ⁶⁸:

- 1) Enrolled in or planning to enroll in a conflicting trial
- 2) Receiving a bi-ventricular ICD device
- 3) New York Heart Association class IV heart failure
- 4) Cardiogenic shock or symptomatic hypotension while in stable baseline rhythm,
- 5) Coronary artery bypass graft (CABG) or percutaneous transluminal coronary angioplasty (PTCA) within the past 3 months
- 6) An MI within the past 40 days
- 7) Clinical symptoms or findings that would make them a candidate for coronary revascularization
- 8) Irreversible brain damage from pre-existing cerebral disease
- 9) Any disease other than cardiac disease (e.g. cancer, uremia, liver failure), associated with a likelihood of survival less than 1 year
- 10) Circumstance that would prevent completion of the trial and follow-up activities, including medical condition

Regarding co-enrollment in CSP#592 and another trial: in order both study chairs must concur on the dual-enrollment. Both chairs must agree that the co-enrollment does not adversely effect the rights or well-being of the participant, and by either the sponsor (CSPCO) or by one or more of the studies. It is the responsibility of the Principal Investigator or Local Site Investigator

to determine if it is appropriate for a participant to be in more than one study concurrently. This may require, contacting the Principal Investigator of the other study to determine appropriateness. Where practicable, the LSI is encouraged to discuss with the Study Chair and the Executive Committee.

C. Inclusion of Women and Minorities

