Strict adherence to the protocol is expected of every participating center and monitored by the DMC, the Executive Committee and the Study Group. Data quality and the completeness of data retrieval, including the Screening Tracker, are closely monitored on an ongoing basis by the WH-CSPCC. The Study Biostatistician presents interim monitoring reports, overall and by site, to the Executive Committee and DMC that include the following types of information: recruitment of participants, characteristics of the population, completeness of data retrieval, and data quality. If a site is identified as an outlier in terms of data quality, a site conference call or site visit is initiated to assess the reasons that problems are occurring and how they can be corrected. If the problems continue, the site may be placed on probation or terminated from the study if the problems cannot be corrected.

F. Monitoring Participant Safety

The local site investigator is responsible for following adverse event reporting requirements as outlined below in the Protocol. These responsibilities include: 1) reviewing the accuracy and

completeness of all adverse events reported, 2) compliance with IRB policies for reporting adverse events and/or serious adverse events, and 3) closely monitoring research participants at for Adverse Events (AEs) or Serious Adverse Events (SAEs). All AEs and SAEs are recorded on the appropriate event form(s). Active monitoring of SAEs begin as soon as the study participant provides consent and continue until the participant completes follow-up. In this study, we will only monitor AEs for 30 days post-randomization (OMT arm) or 30 days post-implantation (OMT + ICD arm). We identify several SAEs that will not require immediate reporting to CIRB, in order to enable detection of clinically meaningful safety information. These SAEs include

- Bleeding/Hematoma
- Incisional pain
- Infection: ICD pocket or lead; requiring antibiotic treatment or explant
- Infection: Other, requiring antibiotic treatment
- Lead dislodgement
- Lead fracture
- Pacing parameters require lead replacement or revision
- Pneumothorax
- Myocardial infarction (MI)
- Stroke
- Tachyarrhythmia/atrial fibrillation

Unexpected SAEs will follow regulations for timely reporting to CIRB: All Serious Unanticipated Problems involving risks to subjects or others and all Serious

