- Complying with study policies as well as IRB policies for reporting adverse events, serious adverse events, and unanticipated adverse device effects
- Report to CSP all SAEs within 72 hours of becoming aware of the event
- Reporting to the IRB safety issues reported to the site by the Sponsor
- Closely monitoring research subjects for any new AEs, UADEs, and SAEs
- Maintaining clinic lists to facilitate near-real time event discovery
- Provide updates to Central Follow-Up Office upon event discovery and upon their request during event follow-up

B. Definitions

1. Adverse Event (AE)

An Adverse Event (AE) is defined as “any untoward physical or psychological occurrence in a human subject participating in research.” An AE can be any unfavorable and unintended event, including an abnormal laboratory finding, symptom, or disease associated with the research or the use of a medical investigational test article. While an AE does not necessarily have to have a

causal relationship with the research ¹²⁰, in CSP #592 AEs will be collected, and only for 30 days after implantation (within the ICD + OMT arm), or 30 days after randomization (OMT arm). We will also collect AEs for 30 days after any re-implantation procedure. For the purposes of this study, we are primarily interested in the following AEs:

- Discomfort at the implant site
- Cosmetic issues (e.g. scars, etc.)
- Psychological issues (e.g. apprehension of an activation, etc.)
- Technical issues related to the device (e.g. actions that may require re-implantation or a generator change)
- Delay angioedema with cough
- Rise in creatinine
- Fatigue
- Slow heart rate

Other adverse events –including those that may not necessarily have to have a causal relationship with this treatment– may also be collected.

2. Unanticipated (or Unexpected) Adverse Event (UAE)

An Unanticipated (or Unexpected) Adverse Event (UAE) is an AE that is new or greater than previously known, in terms of nature, severity, or frequency of occurrence, as documented in the protocol or other materials approved by IRB. Such materials may include, but are not limited to: the informed consent form, clinical investigator’s brochure, and product labeling ¹²⁰.

3. Unanticipated Adverse Device Effect (UADE)

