The Clinical Research Pharmacist and Study Biostatistician generate tabulations of adverse events and present a summary of all AEs and SAEs to the DMC on a schedule set by the DMC. The DMC also determines when they should be unblinded to treatment assignment in reviewing adverse event data. The Study Biostatisticians provides the appropriate data to the DMC at specified intervals for this purpose. Serious adverse events are reported on a regular basis to the DMC for their review. Unanticipated serious adverse events are reported to the DMC as soon as they become known based upon the consensus of the Principal Proponent, the Study Biostatisticians, the Director of the West Haven CSPCC, and the Study Pharmacist.

C. AE/UADE and SAE Monitoring and Reporting

AEs, UADEs and SAEs will be monitored at the study sites throughout the period of the study, beginning as soon the research subject signs the Informed Consent and continuing through end-of-study for each participant. Reportable AEs will be collected and recorded on the appropriate case report form; though we note that while AEs will be continually monitored for closure, new AEs will only be collected for the relevant 30-day window. All UADE and SAEs, including both those related to the study intervention and those not related to the study intervention will be collected and recorded on the appropriate case report form; new UADEs and SAEs will be collected throughout the study. For the purpose of safety monitoring, the study intervention is defined as “ICD implantation” or “Optimal Medical Therapy”.

All UADEs/SAEs require expedited reporting. An SAE case report form will be completed and submitted via the data capture system within 72 -hours of the Site Investigator initially becoming aware of the event. The Study Pharmacist at CSPCPRCC will be responsible for evaluating all SAEs/UADEs for participant safety concerns in a timely manner.

UADEs/SAEs that suggest evidence of a causal relationship between one of the study interventions and the adverse medical event and is unexpected will be reviewed by the Study Leadership Team (i.e., Study Chairperson, Study Biostatistician, Study Project Manager, and the Study Pharmacist) prior to notifying VA Central Office.

< This page left intentionally blank >

XV. BIostatistical Considerations

A. Sample Size

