2.2.9 Analysis of Safety Data

New Adverse Events (AEs) will be collected for only 30 days post-randomization (OMT arm) or 30 days post-implantation (ICD arm); these events will be followed throughout the study until study close or AE resolution, but new AEs will not be collected after this period. All reportable non-serious and serious adverse events will be coded by one or more AE specialist. The total number of AE/SAE, and total number of participants experiencing an event will be summarized by treatment. The proportion of participants experiencing an AE/SAE will be calculated for each treatment group. A chi-square test for the difference in the proportion of SAEs will be used to compare treatment groups over all at the 0.05 level. Treatment comparisons will be made for the number of participants experiencing SAE, the number of treatment-related SAE, and for the number of non-serious adverse events.

In addition, the adverse events will be summarized according to the Medical dictionary for Regulatory Activities (MedDRA)³⁷, in terms of system organ class and preferred terms, by treatment and as overall (Tables 17 and 20).

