Severity of this AE			
Mild			
Moderate			
Severe			
AE Attribution to ICD device			
Not Attributed			
Possibly Attributed			
Yes, Attributed			
AE Attribution to OMT			
Not Attributed			
Possibly Attributed			
Yes, Attributed			
Outcome of AE			
Ongoing, Recovering/Resolving			
Recovered/resolved			
Recovered/resolved with sequelae			
Ongoing, not recovered/not resolved			
Unknown			

* For the control arm, it is within 30 days of randomization.

Table 16: Summary of Adverse Events– All randomized subjects after randomization

	Treatment 1	Treatment 2	All
	N(%)	N(%)	N(%)
No. Subjects Randomized			
Subject-Months of Treatment Exposure			
No. Adverse Events			
No. Subjects with Adverse Events			
AE Criteria			
Emergency room or unscheduled clinic visit for heart failure			
Persistent painful implant site			
New symptomatic dizziness			
New symptomatic fatigue			
Psychological distress			
Other			
Severity of this AE			
Mild			
Moderate			
Severe			
AE Attribution to ICD device			
Not Attributed			
Possibly Attributed			
Yes, Attributed			
AE Attribution to OMT			
Not Attributed			
Possibly Attributed			
Yes, Attributed			
Outcome of AE			
Ongoing, Recovering/Resolving			
Recovered/resolved			
Recovered/resolved with sequelae			
Ongoing, not recovered/not resolved			
Unknown			

Table 17: Summary of Adverse Events after Randomization by System Organ Class and Preferred Term – All Randomized Participants

	Treatment 1		Treatment 2		All	
	N	%	N	%	N	%
System Code						

Table 18: Summary of Serious Adverse Events occurring 30 days of Randomization (OMT) or Implantation (OMT + ICD) – All randomized subjects after randomization

	Treatment 1	Treatment 2	All
	N(%)	N(%)	N(%)
No. Subjects Randomized			
Subject-Months of Treatment Exposure			
No. Serious Adverse Events within 30 days			
No. Subjects with Serious Adverse Events within 30 days			
SAE Criteria *			
Death			
Life Threatening			
Congenital anomaly/birth defect			
Disability-incapacity			
Hosp/Prolongation of Hosp			
Other			
SAE being reported			
Bleeding/Hematoma			
Infection: ICD pocket or lead			
Infection: other			
Pacing parameters required lead replacement or revision			
Pnuemothorax			
Myocardial infarction (MI)			
New onset Atrial Fibrillation/Atrial Flutter			
Stroke			
Other			
SAE Attribution to ICD device			
Not Attributed			
Possibly Attributed			
Yes, Attributed			
SAE Attribution to OMT			
Not Attributed			
Possibly Attributed			
Yes, Attributed			
Outcome of SAE			

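### Non-serious AEs are compared between arms over 30-day windows with different starting points (randomization for OMT, implantation for ICD + OMT), and SAP Table 18 does the same for 30-day SAEs

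*Combined protocol and SAP*

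**What the plan says.** **Non-serious AEs.** Protocol XII.F: "we will only monitor AEs for 30 days post-randomization (OMT arm) or 30 days post-implantation (OMT + ICD arm". Protocol XII.G and XIV.B.1 repeat the rule. SAP 2.2.9 has it as "New Adverse Events (AEs) will be collected for only 30 days post-randomization (OMT arm) or 30 days post-implantation (ICD arm" and adds that nothing new is collected afterwards. XIV.B.1 also opens further windows: "We will also collect AEs for 30 days after any re-implantation procedure". Protocol X.B.5 (Re-implantation) plans two analyses, one limited to the first implant (index AEs) and one covering every implant (all AEs).

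**Comparison.** Protocol XV.C.5 includes non-serious AEs in chi-square testing at the 0.01 level. SAP 2.2.9 lists the number of non-serious AEs among the treatment comparisons. SAP Table 15 reports AEs on the split windows and lists the number randomized.

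**SAEs.** Protocol XII.F: "Active monitoring of SAEs begin as soon as the study participant provides consent and continue until the participant completes follow-up". Protocol XIV.C: "new UADEs and SAEs will be collected throughout the study". The test in SAP 2.2.9 is "A chi-square test for the difference in the proportion of SAEs will be used to compare treatment groups over all". Table 19 counts SAEs after randomization in everyone randomized. The one exception is "Table 18: Summary of Serious Adverse Events occurring 30 days of Randomization (OMT) or Implantation (OMT + ICD").

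**Delay to implant.** Protocol X.B.1 sets a target of a week or less, partly to make the two AE windows compatible. SAP 2.2.4 expects some delay and gives no length.

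**The concern.** A randomized safety comparison needs the same time origin in both arms. Here day 1 of the OMT window is the day of randomization, and day 1 of the ICD window is a later, post-randomization event that not every ICD-arm patient reaches. Three consequences follow for non-serious AEs.

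- ICD-arm AEs before implant are never recorded, so no later analysis can recover them. Table 16, headed as AEs after randomization, can hold only what was collected.
- The ICD window is conditional on surviving to, and accepting, the implant.
- A never-implanted ICD-arm patient has no window, yet seems to remain in the number randomized, where he or she can only count as event-free.

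The arms are compared over windows of equal nominal length placed at different times after randomization. If the background AE rate is not constant over the first weeks, the comparison mixes the effect of the device with the effect of calendar position. Protocol V.A adds "This study will allow the recruitment of inpatients", so a changing early rate is possible, though nothing in the documents quantifies it. Early harm is a main cost to set against any mortality benefit, so the table that shows it should be a clean randomized contrast.

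**Working it through.** **1. Are the windows aligned anywhere?** For SAEs, yes: collection from consent, an overall test, and Table 19 from randomization. For non-serious AEs, no: protocol XII.F, XII.G and XIV.B.1 and SAP 2.2.9 all use the split origin, and so does Table 15. SAP 2.2.4 shifts the OMT start by the mean implant delay, but only in a sensitivity analysis of mortality endpoints.

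**2. How long can the delay be?** One week is a target. SAP 3.2 requires the first contact in the ICD arm to be at least 30 days after implant and no later than day 120 after randomization, so the visit rules accommodate implants up to day 120 − 30 = 90.

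**3. Does the plan's own model reproduce?** Inputs (SAP 2.1): 1,462 patients; 102 followed 5 years; 1,360 accrued over 3 years with 2 to 5 years' follow-up; control mortality 15% per year; HR 0.75; drop-in 2.5% per year; drop-out 1% in year 1; loss 1% per year. A daily-step Markov log-rank calculation gives 564.7 events and 90.1% power, against the stated 565 and 90%. Without the 1% loss it gives 574.5 events and 90.6%. The same model gives about 47 OMT patients implanted during follow-up (47/731 = 6.4%) and about 7 ICD-arm drop-outs. The 7 include explants, so at that rate they are an upper bound for never-implanted patients.

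**4. Deaths and the Table 18 window.** The control hazard is −ln(0.85) = 0.1625 per year. Expected deaths among 731 in d days = 731 × (1 − exp(−0.1625 × d/365)).

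| Mean delay d | ICD-arm deaths before the window opens |
|---|---|
| 7 days | 2.3 |
| 14 days | 4.5 |
| 30 days | 9.7 |

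OMT deaths inside the 30-day window: 731 × (1 − exp(−0.1625 × 30/365)) = 9.7.

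These are the events left out, not the net change in the table, because the ICD window also runs later. Suppose HR 0.75 applies at once after implant (hazard 0.75 × 0.1625 = 0.1219) with no procedural deaths. At a 7-day delay the ICD row of Table 18 would show (731 − 2.3) × (1 − exp(−0.1219 × 30/365)) = 7.3 deaths. Counted from randomization it would show 2.3 + (731 − 2.3) × (1 − exp(−0.1219 × 23/365)) = 7.9. At a 30-day delay the figures are (731 − 9.7) × (1 − exp(−0.1219 × 30/365)) = 7.2 and 9.7.

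**5. Non-serious AEs (assumed rates only).** Assume a proportion r of patients has a background non-serious AE per 30 days, at a constant rate. Patients with an uncollected pre-implant AE = 731 × (1 − (1 − r)^(d/30)).

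| r | 7 days | 14 days | 30 days |
|---|---|---|---|
| 5% | 9 | 17 | 37 |
| 10% | 18 | 35 | 73 |

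**6. Never-implanted patients.** If a share p has no window but stays in the denominator, the reported proportion is the true proportion × (1 − p). A true 10% reads 9.9% at p = 1% and 9.5% at p = 5%. The values of p are assumed.

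**7. OMT crossover implants.** X.B.5 says AEs are collected following any implant, but under a re-implantation heading. XIV.B.1 ties the implant window to the ICD + OMT arm. SAP 2.2.9 closes collection after the single window, which also conflicts with the re-implant windows in XIV.B.1. The texts do not settle whether the roughly 47 crossover implants have an AE window.

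**The case against.** The strongest reply is that the events that matter most are safe. A reader might infer that SAEs are also collected for only 30 days, or that the SAE test rests on mismatched windows. The documents do not support that: SAEs run from consent to the end of follow-up, the chi-square is overall, and Table 19 counts from randomization in all randomized patients. Only Table 18, a descriptive shell with no test column, is distorted, and it can be rebuilt, since SAP 3.5 holds time from randomization or implantation to onset. No death is lost to the trial. This part of the reply stands in full.

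Other stronger readings also fail. Never-implanted patients are not dropped from Tables 15 and 18; they appear to be counted with no window. That the crossover implants have no AE window is one reading of conflicting texts. Repeat windows in the ICD arm do not spoil every AE analysis, because the index-AE analysis in X.B.5 uses the first implant only.

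It can also be said that the split is deliberate and disclosed, that several AEs of interest cannot occur before an implant, and that entry requires stability on OMT, so a high early risk in inpatients is conjecture. These points justify keeping an implant-anchored table. They do not justify using it as the between-arm comparison, because a one-week target does not make the origins equal and nothing in the AE analysis corrects for the difference.

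**Conclusion.** The concern holds for non-serious AEs and for SAP Table 18, and not beyond them. ICD-arm non-serious AEs before implant go uncollected, never-implanted patients have no defined window, and the arms are nevertheless compared on these data.

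For Table 18, about 2 (7-day mean delay) to about 10 (30-day delay) expected ICD-arm deaths fall outside the window, against about 10 OMT deaths inside it. This assumes the plan's 15% annual mortality applies evenly from randomization. The net change in the death count is smaller, roughly 0.6 to 2.5 on the assumptions in step 4.

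For non-serious AEs the documents give no rate. On an assumed 5% to 10% per 30 days, the loss is 9 to 18 patients at a 7-day delay and 37 to 73 at 30 days. These counts measure what goes unrecorded. They do not fix the size or direction of bias in the test, which depends on how the early AE rate changes and on how many patients are never implanted. The change is worth making because it is cheap and because uncollected AEs cannot be recovered.

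**What to change.** 1. In protocol XII.F, XII.G and XIV.B.1 and SAP 2.2.9, collect non-serious AEs from randomization in both arms through the same fixed day, ascertained at the first contact on or after that day. Base the between-arm AE comparison and Table 15 on that window for all randomized patients, and state that never-implanted ICD-arm patients are included.
2. Re-cut Table 18 from randomization in both arms, using SAE data already collected.
3. Keep 30 days after implantation as a separate, descriptive per-procedure table for every implanted participant. It also covers late implants, whose procedural window may run past the fixed day.
4. Reconcile protocol X.B.5 and XIV.B.1 with SAP 2.2.9 on whether AEs after an OMT crossover implant, and after re-implantation, are collected.

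**Cost.** Wording changes, one re-programmed table, and some additional AE forms for the added days. No extra patients or visits are needed. The existing 1-4 month contact does not guarantee coverage: SAP 3.2 allows it at day 30, so with a later fixed day (day 60, say) some patients would report at the 6-month contact. Some AEs would then be recalled after a longer interval, and the choice of day should weigh that against how much of the implant period it covers.

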Unanticipated SAEs as defined by VHA Handbook 1058.01 will be reported to the CIRB within 5 business days of becoming aware of the problem or event.

Sites will be responsible for safety surveillance in order to capture serious adverse events in a timely manner, e.g. through alerts in the local medical record or periodic searches of the medical record for hospitalizations. Whomever encounters news of an event must report that event via the proper reporting pathways (SAE case report form, and when appropriate for unexpected and related problems: Form 119 to Central IRB). The sites and Central Follow-Up office are asked to notify each other of event discovery for maximum efficiency. Once the initial event report has been processed, its 30-day follow-up will be the responsibility of the Central Follow-Up Office.

G. Adverse Event Definition and Monitoring

While an AE does not necessarily have to have a causal relationship with the research, in CSP #592 only non-serious AEs will be collected, related to the treatment of heart failure. Adverse Events will be collected for 30 days after implantation (OMT + ICD arm) or 30 days post-randomization (OMT arm). Relatedness involves an assessment of the degree of causality (attributability) between the study intervention and the event. Site investigators are asked to provide an assessment of relatedness. All AEs with a reasonable causal relationship to the investigative treatment should be considered “related” and will be collected. A definite relationship does not need to be established. AEs are defined in Section XIV.

H. Serious Adverse Event Definition and Reporting

Serious Adverse Events (SAEs) are defined in Section XIV. All SAEs whether or not they are considered related will be collected in CSP #592. Site investigators will still be asked to provide an assessment of relatedness as the assessment provided by the site investigator is part of the information used by the sponsor to determine if the SAE presents a participant safety concern. Any SAE that originally started as a non-serious AE that was not reported at the time of the event because it was considered unrelated will be reported within 72 hours of becoming an SAE as defined above regardless of relatedness.

I. Minimizing Attrition

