The total number of SAE will be summarized by treatment. The proportion of participants experiencing an SAE will be calculated for each treatment group. A chi-square test for the difference in the proportion of SAEs will be used to compare treatment groups over all at the 0.05 level, and with subgroupings of SAEs and non-serious AEs at the 0.01 significance level. Treatment comparisons will be made for the number of participants experiencing SAE, the number of treatment-related SAE, and for the number of non-serious adverse events.

6. Exploratory Analyses

Additionally, data from the Informed Consent Questionnaire will be used for exploratory analysis of the association between perceived and actual participant understanding of the study. ICDs are capable of delivering information related to a wide range of parameters including activity level, heart rate variability and battery and lead status. Descriptive analysis will be used to summarize the ICD device data. The analysis will be limited in scope to three activities:

- Routine assessment of device activations to assess shock events;
- Device interrogation upon death; and

- Analysis of device data at follow-up appointments as is done in standard clinical practice.

These activities contribute substantially to optimal medical therapy.

7. Consenting Rates

Whereas there are no known published data on the willingness of elderly patients to consent into a study of this nature, it is incumbent on CSP#592 to measure and report the rates of consent among patients deemed so eligible. Data collected from patients found eligible for entry into the study will be analyzed for rate of consenting into the study, as well as rationale for non-matriculation. This activity contributes substantially to the knowledge base for the design of future clinical trials both in the study of the elderly, and in device-based trials.

XVI. FEASIBILITY

A. Estimating the Patient Population

1. ICD Candidacy among VA Patients

a) Candidacy Criteria

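### Non-serious AEs are filtered by the unblinded site's judgement of relatedness in XII.G and XII.H but not in XII.F, and are then compared between arms, so the comparison can mix harm with attribution

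*Combined protocol and SAP*

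**What the plan says.** The protocol and SAP give several rules for which non-serious AEs enter the database.

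- **Related only.** Protocol XII.G: "in CSP #592 only non-serious AEs will be collected, related to the treatment of heart failure". The same paragraph says "Site investigators are asked to provide an assessment of relatedness", and that events with a reasonable causal link are the ones collected. XII.H follows the same rule: it provides for "Any SAE that originally started as a non-serious AE that was not reported at the time of the event because it was considered unrelated".
- **All.** Protocol XII.F sets no relatedness condition ("All AEs and SAEs are recorded on the appropriate event form(s"), only a 30-day limit for AEs.
- **Optional.** Protocol XIV.B.1 lists AE types of main interest. It adds that others, including those that "may not necessarily have to have a causal relationship with this treatment", may be collected too.
- **Undefined.** Protocol XIV.C and SAP 2.2.9 refer to reportable AEs without saying whether relatedness makes an event reportable.

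Both documents then compare arms. Protocol XV.C.5 plans a chi-square test "with subgroupings of SAEs and non-serious AEs at the 0.01 significance level". SAP 2.2.9 plans treatment comparisons for "the number of treatment-related SAE, and for the number of non-serious adverse events", but states a level, 0.05, only for the overall SAE test. Protocol IX.B says that neither participants nor site personnel are blinded. All SAEs are collected whether or not they are thought related (XII.H, XIV.B.4).

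**The concern.** A relatedness filter applied by someone who knows the arm can act differently in the two arms. One arm has just had a procedure; the other continues a therapy on which patients had to be stable before entry. The same fatigue or creatinine rise could be judged related in one arm and not in the other, and so be recorded in one and lost in the other.

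The planned comparison would then partly reflect how sites attribute events. Because the sections disagree, sites may also apply different rules, so the distortion could vary by site. Events never reported cannot be reliably recovered at analysis. The filter also works against the protocol's own aim in X.B.1, where implant timing is set partly to make the AE windows of the two arms comparable.

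**Working it through.** **Do the sections conflict?** Take a fatigue episode on day 10 that the investigator considers unrelated. Under XII.F it is recorded. Under XII.G it is not, and XII.H treats its absence as expected. That is an outright conflict. XIV.B.1 is only permissive and fits either practice, so it adds latitude without settling the matter. XIV.C and SAP 2.2.9 do not settle it either, because reportable is undefined. XII.G also shifts what an event must be related to: heart failure treatment, the study intervention, then the investigative treatment. XIV.C defines the study intervention as either ICD implantation or OMT.

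**What the filter does.** Let p1 and p0 be the true proportions with a non-serious AE in the window (ICD arm, OMT arm), and a1 and a0 the proportions of those judged related and therefore recorded. As a simplification, attribution is applied per participant.

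- Observed risk in each arm = p × a
- Observed risk ratio = (p1/p0) × (a1/a0)

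Without a filter, a1 = a0 = 1 and the second factor disappears.

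**How large could it be?** The plan states no AE rate, attribution rate or AE power, so there is no figure to reproduce. Inputs from the documents are n = 731 per arm (protocol III.E) and two-sided alpha 0.01 (XV.C.5). Assumed inputs are p1 = p0 = 10%, 20% or 30%, with attribution of 50% v 40% or 60% v 40%.

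With q = p × a, and q̄ the mean of q1 and q0:

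- SE0 = √[2q̄(1 − q̄)/n]
- SE1 = √{[q1(1 − q1) + q0(1 − q0)]/n}
- P(reject) = Φ[(|q1 − q0| − 2.576 × SE0)/SE1]

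Example, true risk 20% and attribution 60% v 40%: q1 = 0.12, q0 = 0.08, q̄ = 0.10. SE0 = √(2 × 0.10 × 0.90/731) = 0.01569. SE1 = √[(0.1056 + 0.0736)/731] = 0.01566. (0.04 − 2.576 × 0.01569)/0.01566 = −0.027, and Φ(−0.027) = 0.49.

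| True risk, both arms | 50% v 40%: observed | P(reject) | 60% v 40%: observed | P(reject) |
|---|---|---|---|---|
| 10% | 5% v 4% | 0.05 | 6% v 4% | 0.21 |
| 20% | 10% v 8% | 0.11 | 12% v 8% | 0.49 |
| 30% | 15% v 12% | 0.19 | 18% v 12% | 0.74 |

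The nominal rate is 0.01. The observed risk ratios are 0.50/0.40 = 1.25 and 0.60/0.40 = 1.5, against a true ratio of 1. If 0.05 were used instead, the ranges would be 0.15 to 0.39 and 0.42 to 0.90.

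**The case against.** The strongest reply is that the harm is asserted rather than documented. Both arms receive OMT and OMT counts as a study intervention, so an event can qualify as related in either arm. The threshold is low, since XII.G does not require a definite relationship. No text shows that sites would attribute differently by arm. Form 17 and the Operations Manual, which might settle practice, are not among the documents available. This stands as a limit on size and direction: the attribution gaps above are assumptions, and bias against the ICD is plausible but not established. It does not remove the conflict between XII.F and XII.G.

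Four stronger readings are tempting and are not supported.

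- **That the comparison measures attribution instead of harm.** It measures their product. It is attribution alone only if true risks are equal, which is unlikely for total counts: implant-site discomfort and device technical problems essentially need a device.
- **That the not-attributed rows in SAP Tables 15 and 16 show unrelated AEs are expected.** Each table has one attribution block for the device and another headed "AE Attribution to OMT". An event attributed to one can be unattributed to the other, so the rows are needed under either rule.
- **That a site cannot comply with both XII.G and XIV.B.1.** It can, because XIV.B.1 is optional. The outright conflict is with XII.F.
- **That false rejection would be near certain.** Wider assumed gaps do give high figures (70% v 40% gives 0.48 to 0.98), but nothing in the documents supports gaps of that size.

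**Conclusion.** The point holds as an unreconciled collection rule feeding a planned between-arm comparison. Where XII.G is followed, the non-serious AE comparison mixes harm with open-label attribution, and the mix may differ by site. If every site follows XII.F, this filter does not arise.

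The false-positive figures illustrate modest to moderate attribution gaps; they are not estimates for this trial. They assume equal true risks, full planned enrolment and a single proportion tested at 0.01. Since XV.C.5 may mean subgroupings of non-serious AEs, rarer types would lie towards or below the 10% row. The 0.01 level for non-serious AEs appears only in the protocol.

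The scope is non-serious AEs in the 30-day windows. The filter does not touch the SAE comparison or all-cause mortality. It should still be corrected, because safety is part of the study's stated aim and the protocol already has a relatedness-neutral rule for SAEs.

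**What to change.** 1. State one rule in XII.F, XII.G, XIV.B.1, XIV.C and SAP 2.2.9: non-serious AEs in the 30-day window are collected in both arms regardless of relatedness, and attribution is recorded separately and is not a condition of collection.
2. Amend the XII.H clause on AEs left unreported because they were considered unrelated; otherwise it will contradict the new rule.
3. Align the AE list in XIV.B.1 with SAP Tables 15 and 16. XIV.B.1 names creatinine rise, slow heart rate and angioedema with cough, which have no rows in the tables. The tables name new dizziness and emergency or unscheduled heart failure visits, which XIV.B.1 omits.
4. Report device-only types (implant-site discomfort, cosmetic and technical issues) descriptively, and limit the between-arm test to types that can occur in either arm. State its level in the SAP.

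If related-only collection is kept, drop the between-arm test of non-serious AEs and label the counts descriptive.

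The cost is wording changes in both documents, edits to the table shells and possibly the AE form, and some extra AE forms in a short window. No visits are added. The rule needs settling before or during collection.
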